5. Pharmacokinetic samples for GSK3342830 and potential metabolites will be collected on Day 1 at the following time points: pre-dose (within 15 minutes before dosing) and 0.5, 1 (end of infusion), 1.25, 1.5, 2, 2.5, 3, 3.5, 4, 4.5, 5, 6, 8, 10, 12, 16, and 24 hours after the start of infusion. Single pre-dose trough samples will be taken on the mornings of Days 3, 6, 9, 12, and 13. Serial samples will be collected on Day 15 at the following time points: pre-dose (within 15 minutes before dosing) and 0.5, 1 (end of infusion), 1.25, 1.5, 2, 2.5, 3, 3.5, 4, 4.5, 5, 6, and 8 hours after the start of infusion. At the end of the study, the saved blood samples from a predicted therapeutically-relevant dose level and higher dose level for plasma PK analysis of parent and from the highest dose level completed for potential metabolite profile will be transferred to a GSK specified laboratory. Details of PK sample

collection and storage will be provided in the Study Reference Manual.

6. Pooled urine samples will be collected on Day 1 and Day 15 over the following time intervals: pre-dose (within a 24-hour period before dosing, may begin on Day -1) and 0 to 8 and 8 to 24 hours post-dose. Two aliquots of urine samples for baseline analysis may be collected from any time after admission to just before dosing on Day 1. At the end of the study, the saved urine samples from a predicted therapeutically-relevant dose level and higher dose level for urinary PK analysis of parent and from the highest dose level completed for potential metabolite profile, will be transferred to a GSK specified laboratory. Urine will be collected in opaque bottles to maintain blind of blinded study site personnel. Details of urine sample collection and storage will be provided in the Study Reference Manual.
7. Continuous dual-lead telemetry will be initiated on Day -1 at least 8 hours before treatment administration on Day 1 and will continue until 48 hours post dose.
8. Subjects will be discharged from the clinical unit after the Day 16 assessments are complete.

Table 6 Time and Events Table: Follow-up Visit; Single and Repeat Dose Escalation (Part 1 and Part 2) and Single Dose (Part 3)

Procedure	Follow-up Visit (7 to 10 days post last dose or early termination)
Adverse event/serious adverse event review	X
Concomitant medication review	X
Brief physical examination	X
12-lead electrocardiogram	X
Vital signs	X

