
 
To evaluate whether steady state was achieved, statistical analysis of steady-state <math>C_\tau</math> will be performed after log-transformation of <math>C_\tau</math> on Days 3, 6, 9, 12, 13, and 15. A mixed effect model will be fitted by dose and day (as a continuous covariate) as a fixed effect term and subject as a random effect term. Distributional assumptions underlying the statistical analyses will be assessed by visual inspection of residual plots. Normality will be examined by normal probability plots, while homogeneity of variance will be assessed by plotting the residuals against the predicted values for the model. Alternative analyses of the data will be performed if any of the model assumptions appear to be violated.
 

Model Checking & Diagnostics

 
Refer to Appendix 9: Model Checking and Diagnostics for Statistical Analyses.
 

Model Results Presentation

 
The coefficients for the slope of the day effect on the log-scale will be used to evaluate steady-state for each dose group. Using the pooled estimate of variance, the 90% CIs for the slope will be calculated.
 

Model Results Presentation

 
The least squares geometric mean ratio and 90% CI for the comparison of <math>AUC(0-t)</math>, <math>AUC(0-\infty)</math> and <math>C_{max}</math> from Japanese subjects (Part 3) to subjects of non-Japanese heritage of the same dose level (Part 1) will be calculated.
 

Assessment

 
Assessment of GSK3342830 PK in healthy adult Japanese subjects vs the same dose level of
 

Pharmacokinetic Statistical Analyses
healthy adult subjects in Part 1.
Endpoint(s)

• The geometric mean ratio and associated 90% CI for Part 3 vs Part 1.

Model Specification

• To evaluate whether there is a difference in the PK parameters in healthy adult Japanese subjects, a fixed effect model will be fitted with Study Part as fixed effect.

Model Checking & Diagnostics

• Refer to Appendix 9: Model Checking and Diagnostics for Statistical Analyses.

Model Results Presentation

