Summary of Statistical Analysis of GSK3342830 Plasma Time Invariance in Part 2

Dose: XX mg

Parameter (Unit)	Day	N	Geometric LS Means	Regimen Comparison	Ratio of Geometric LS Means (%)	90% Confidence Interval of Ratio (%)	CVw(%)
AUC(0-inf) (Unit)	1	xx	x.xxx	15/1	x.xxx	(x.xxx, x.xxx)	x.xxx
AUC(0-tau) (Unit)	15	xx	x.xxx				

*Notes to programmer: Repeat for each dose level.*

Note: A linear mixed-effect model with group (group=1 for AUC(0-inf) on Day 1, and group=2 for AUC(0-tau) on Day 15) as a fixed effect and subject as a random effect was fitted to the natural log transformed PK parameters.

Source Data: Listing 46.

GlaxoSmithKline

Example : PK\_T1  
Protocol : 204847  
Population : PK Parameter

Page 1 of n

Table 3.12  
Summary of Statistical Analysis of GSK3342830 Plasma Accumulation Ratio in Part 2

Parameter (Unit)	Dose* (mg)	Day	N	Geometric LS Means	Regimen Comparison	Ratio of Geometric LS Means (%)	90% Confidence Interval of Ratio (%)	CVw(%)
AUC(0-tau) (Unit)	xx	1	xx	x.xxx	15/1	x.xxx	(x.xxx, x.xxx)	x.xxx
		15	xx	x.xxx				
	yy	1	xx	x.xxx	15/1	x.xxx	(x.xxx, x.xxx)	
		15	xx	x.xxx				
	zz	1	xx	x.xxx	15/1	x.xxx	(x.xxx, x.xxx)	
		15	xx	x.xxx				

Note: A linear mixed-effect model with dose, day, and dose-by-day interaction as fixed effects and subject as a random effect was fitted to the natural log transformed PK parameters.

\* If dose-by-day interaction is significant (p-value less than 0.05), then point estimate and 90% CI will be reported for each dose level.

Source Data: Listing 46.

GlaxoSmithKline

Example : PK\_T1  
Protocol : 204847  
Population : PK Parameter

Page 1 of n

Table 3.13  
Summary of Statistical Analysis of GSK3342830 Plasma Steady State Assessment in Part 2

Parameter	Days Included	Estimated Slope for Day	90% CI Lower-Upper
Ctrough (units)	3, 6, 9, 12, 13, 15	x.xxx	x.xxxx-x.xxxx

Note to programmer: If the 90% CI does not include zero, repeat the analysis without the data for the earliest day used in the previous analysis. Display the results for all models run.

Note: A mixed effect model will be fitted by dose and day (as a continuous covariate) as a fixed effect term and subject as a random effect term. No formal statistical hypothesis tested. Steady state is estimated to be achieved by the earliest day included in the analysis when the 90% CI of the slope includes 0.

Source Data: Table 3.06.

GlaxoSmithKline

Example : PK\_T2  
Protocol : 204847  
Population : PK Parameter

Page 1 of n

Table 3.14  

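### The steady-state rule in SAP shell Table 3.13 reads an interval too wide to exclude zero as steady state, so a moderate continuing rise in troughs is usually declared steady.

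*SAP*

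**What the plan says.** Achievement of steady state in Part 2 is part of a secondary objective (protocol section 3), assessed from trough concentrations. The protocol's schedule for Part 2 (section 7.1, Table 5) states: "Single pre-dose trough samples will be taken on the mornings of Days 3, 6, 9, 12, and 13". The Day 15 pre-dose sample completes the set.

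SAP section 8.1.3.2 gives the model for log trough: "A mixed effect model will be fitted by dose and day (as a continuous covariate) as a fixed effect term and subject as a random" (the quotation stops mid-sentence; subject is the random factor). It continues: "The coefficients for the slope of the day effect on the log-scale will be used to evaluate steady-state for each dose group", and "Using the pooled estimate of variance, the 90% CIs for the slope will be calculated". Protocol section 9.4.2 has the same content. Neither section contains a rule for declaring steady state, and protocol section 9.1 promises estimation, with point estimates and CIs.

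The rule appears only in SAP shell Table 3.13. The programmer note reads "If the 90% CI does not include zero, repeat the analysis without the data for the earliest day used in the previous analysis", followed by "Display the results for all models run". The table footnote reads "No formal statistical hypothesis tested", and then "Steady state is estimated to be achieved by the earliest day included in the analysis when the 90% CI of the slope includes 0". The shell has one slope row and no dose column. It gives no margin, no minimum set of days and no point at which the deletions stop. SAP section 2.1 records no change from the protocol's analysis.

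**The concern.** A CI that includes zero shows that the data do not rule out a flat trough. It does not show that the trough is flat. Under this rule a smaller or noisier cohort reaches steady state sooner, because its interval is wider.

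The loop strengthens the effect. A rise clear enough to exclude zero over Days 3–15 leads to refits on shorter spans with fewer samples, where the same rise becomes harder to detect. The process stops as soon as the interval is wide enough, and the footnote then supplies a date.

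At stake is the steady-state statement in the study report. Troughs still climbing at Day 15 could be reported as steady from, say, Day 9 or Day 12. Because the shell shows a single slope, a drift confined to one dose could also be averaged with flat troughs at the others.

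**Working it through.** The plan states no operating characteristic, margin or trough SD for this rule, so there is no figure of its own to reproduce.

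**Inputs.** Trough days 3, 6, 9, 12, 13 and 15 (protocol Table 5). About 8 active subjects in each of 3 cohorts, so about 24 (protocol section 4.3). 90% two-sided interval (SAP section 8.1.3.2). Assumption, not in the documents: within-subject SD *s* of log trough between 0.1 and 0.5.

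**Interval width.** For complete data with a random subject intercept, the slope has SE = s/√(n·Sxx), where Sxx is the sum of squared deviations of the days kept. For six days the mean is 58/6 = 9.67 and Sxx = 103.33. For Days 13 and 15, Sxx = 2. The half-width is t × SE, here in units of s per day. For n = 24, df = 24(m − 1) − 1 with m days kept:

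| Days kept | Sxx | t (df) | Half-width, n = 24 |
|---|---|---|---|
| 3–15 | 103.33 | 1.658 (119) | 0.033 |
| 6–15 | 50.00 | 1.661 (95) | 0.048 |
| 9–15 | 18.75 | 1.667 (71) | 0.079 |
| 12, 13, 15 | 4.67 | 1.678 (47) | 0.159 |
| 13, 15 | 2.00 | 1.714 (23) | 0.247 |

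The widening is 0.247/0.033, about 7.4-fold. For n = 8 with its own variance the half-width goes from 1.685/√(8 × 103.33) = 0.059 to 1.895/√(8 × 2) = 0.47, about 8-fold.

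**Check by hand.** Take a common slope, s = 0.2 and a true log slope of 0.03 per day. Over Days 3–15 the half-width is 0.033 × 0.2 = 0.007, and the rise is detected. Over Days 12, 13 and 15 it is 0.159 × 0.2 = 0.032, already larger than the true slope. An estimate equal to the truth would then be declared steady.

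**Simulation.** 4,000 trials per setting, troughs rising linearly on the log scale through Day 15, rule applied to the five day sets above. The Day 15/Day 3 ratio is exp(12 × slope). The per-dose reading pools the variance over the three cohorts. Entries are the percentage of trials in which steady state is declared at some step.

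| Rise per day (Day 3 to 15) | Slope per dose, n = 8: s = 0.1 / 0.2 / 0.3 / 0.5 | Common slope, n = 24: s = 0.1 / 0.2 / 0.3 / 0.5 |
|---|---|---|
| 2% (27%) | 87 / 96 / 98 / 99 | 66 / 91 / 95 / 98 |
| 3% (43%) | 73 / 92 / 97 / 99 | 36 / 80 / 90 / 96 |
| 5% (82%) | 40 / 81 / 91 / 97 | 4 / 51 / 76 / 90 |
| 10% (232%) | 1 / 39 / 68 / 86 | 0 / 4 / 28 / 67 |

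A separate run agreed within about three points (common slope at 10% per day: 0, 6 and 31% for s = 0.1, 0.2 and 0.3).

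**What the loop adds.** With n = 8 and s = 0.3, the Days 3–15 fit alone includes zero in 39%, 11% and 0% of trials at 2, 3 and 5% per day. With deletions these become 98%, 97% and 91%.

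**Dating.** If troughs approach a plateau with a 5-day half-life (67% of steady state on Day 9, 86% on Day 15), then with n = 8 and s = 0.3 the rule declares steady state in 96% of trials, and in 47% dates it to Day 9 or earlier. With truly flat troughs, about 10% of trials miss Day 3 by chance and receive a later date.

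**The case against.** A reader might infer that steady state is declared almost whatever the troughs do, or that the rule can hardly ever return a negative answer. Neither follows. With a common slope, a 10% daily rise is declared steady in only 0%, 4% and 28% of trials at s = 0.1, 0.2 and 0.3, and a 5% rise at s = 0.1 in 4%. The rule can also end without a declaration, since a single remaining day has no slope.

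Slow accumulation is also unlikely for this drug. Protocol section 4.5 predicts clearance 0.93 mL/min/kg and volume 0.121 L/kg. In a one-compartment approximation k = 0.93 × 60/1000/0.121 = 0.461 per hour, the half-life is 0.693/0.461 = 1.5 h, and accumulation at 8 h is 1/(1 − exp(−8 × 0.461)) = 1.03. Troughs should be flat well before Day 3. A later rise would suggest changing clearance; in the same approximation, 27% and 43% higher troughs correspond to only about 7% and 11% more AUC. Changing clearance is addressed separately by the accumulation and time-invariance ratios, each with a 90% CI.

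Nor would drift be hidden: every fitted model is displayed, so the Days 3–15 slope is always visible, and Figure 3.05 plots median pre-dose concentration by day.

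These points limit the consequence but do not justify the rule. The half-life is scaled from animals in a first-in-human study, and the objective exists to check such predictions. Stating that no hypothesis is tested does not remove the footnote's declaration and date.

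**Conclusion.** The rule is wrong as written. For a moderate continuing rise it usually declares steady state: about 80–96% of trials with a common slope and about 92–99% with a slope per dose, at 2–3% per day. Both ranges assume a within-subject log SD of 0.2–0.3, linear drift on the log scale and complete data. A smaller SD or a steeper drift lowers them substantially. Most of the false declarations come from the deletions.

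The shell also departs from the text it implements. Protocol section 9.4.2 and SAP section 8.1.3.2 call for a slope and 90% CI for each dose group and no declaration; the shell shows one slope and adds one.

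The consequence is confined to a secondary pharmacokinetic conclusion. A reader might infer that dose escalation is exposed to this rule. It is not: protocol sections 6.3 and 9.3.2 and SAP section 3.1 base escalation on safety, tolerability and exposure (AUC and Cmax), not on Table 3.13.

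**What to change.** In shell Table 3.13, delete the declaration based on the CI including zero, and remove the drop-a-day loop as the basis for any conclusion. Fits on fewer days may stay if labelled descriptive. Add a dose column, with a dose-by-day term in the model so that each dose has its own slope. For each dose report the slope over Days 3, 6, 9, 12, 13 and 15, as percentage change per day and as the model-based Day 15/Day 3 trough ratio, exp(12 × slope), with 90% CI. Base the steady-state statement on that interval, read with Figure 3.05 and the accumulation and time-invariance ratios.

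The work is limited to shell and model wording; no data collection changes. Two things are lost or exposed. There is no automatic day of steady state. And with about 8 active subjects per dose the interval may be too wide for a firm statement: at s = 0.3 the half-width of the log ratio is about 12 × 0.059 × 0.3 = 0.21, a factor of about 1.23 either way.

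A yes/no limit is optional and not part of the required change. With an assumed limit of 0.80–1.25 on that ratio, a 2% daily rise would pass at most about 3% of the time, but truly flat troughs with 8 per dose would pass only 69% of the time at s = 0.2 and 11% at s = 0.3. If the sponsor wants such a limit, it should be fixed before unblinding with that cost accepted.
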